3. Conduct a comprehensive evaluation of the impact of the CATCH-UP program, collaborate closely with other RADx-UP projects in sharing data and adapting processes, and continuously communicate with our community partners to assess effectiveness and disseminate research findings. This evaluation will include measurement and dissemination of data related to 1) Provider-level Outcomes that include knowledge and attitudes of disease prevalence, clinical characteristics including typical and atypical symptoms and disease severity, testing importance and strategies, vaccination, importance and use of personal protective equipment, availability of testing and delays in return of results, and provider observations of patient attitudes and other reported barriers, 2) Care Process Outcomes such as testing, test positivity, and test refusal rates, influenza, pneumococcal, and zoster vaccination rates, 3) Community-level Outcomes that include the number of tests conducted by mobile testing units and the resulting test positivity rate, 4) Patient-level Outcomes such as knowledge and attitudes of disease prevalence, disease characteristics including severity and acute and chronic symptoms, risk perspective and preferences, importance and use of personal protective equipment, patient acceptance of various testing options, and facilitators and barriers to participating in testing and future vaccination programs, 5) Patient Factors such as demographics, social

determinants of health, and clinical characteristics that may be associated with COVID-19 morbidity and mortality disparities or reach of each testing modality, and 6) Qualitative Outcomes including perceptions of facilitators and barriers to testing and the utility, effectiveness, and generalizability of the program, explored through key informant interviews, exit interviews, and in-depth program implementation process observations.

B. Background and Significance

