The CPP will use an established structure of meetings to launch efforts with both virtual and in-person capabilities for participation that CHIOs have utilized with great success and sustainability. Communication platforms managed by the CHIOs represent individuals from all 77 Oklahoma counties with over 3,000 community-based organizations receiving information. Communities will have multiple pathways to request and deploy stationary and mobile testing events to support COVID-19 testing including scheduled events at the county level, requests by individual employers for workplace testing events (including public schools and private businesses), and specific requests by the public health authorities to address urgent hotspots or existing testing deserts. These requests can come directly to the CATCH-UP leadership or CEO Core, to CHIO organizations in their localities, or through existing community partners such as the LCDA and SPTHB, or new partnerships developed as a result of this initiative.

Scope of Testing

CATCH-UP aims to complete more than 250 testing events across Oklahoma, including 88 small events of 25-50 tests, 66 medium events of 51-100 tests, 44 large events of 100-200 tests, 33 x-large events of 200-500 tests, and 22 community-level events of > 500 tests. Each tested individual will be provided a flyer with a description of the initiative and a link to a REDCap survey described above. Mobile testing support will be facilitated by the SPTHB and Oklahoma Caring Foundation through the use of their Caring Vans. The combined fleet of 12 vans will be deployed to support CHIOs and communities in event organizing, event management, staffing support, and further addressing community-level needs. Partners from each of the organizing CHIOs will further identify and recruit community-based organizations to support addressing social determinants of health needs identified during the testing projects, including food insecurity, medication assistance, and utility vouchers. We will adapt to ongoing disease outbreaks and community needs, but anticipate that this aim will result in a minimum of 45,000 viral tests

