performed in the first year of implementation. We also anticipate that early demonstrated successes will allow us to leverage other state or philanthropic funding to increase the number of testing sites and events. At selected events, we will also explore the feasibility of POC diagnostics for future CATCH-UP events as well as collaborate with OMRF to provide limited serologic testing. Both of these facilitate further understanding of how different testing strategies may impact participant attitudes towards COVID-19 and identify additional socioeconomic facilitators and barriers to testing (such as the role of wait time for both testing and return of results).

Supporting the CPP

General testing supplies and laboratory analysis will be provided by the OSDH as part of their existing program for community-based testing and supplemented as described by this project. OSCTR partners and CHIOs will be incentivized and supported to organize testing events in the same manner we have done in other projects. At the initiation of the project, each certified CHIO or OSCTR partner will be provided start-up funds to initiate the program, assist in identifying community barriers and facilitators, and secure community testing sites. For each testing event completed, we will provide additional innovation funding to support the community partner for use in evidence-based activities targeted at addressing COVID-19 related health disparities and social determinants of health. Funding will also be provided to partners to staff and supply events based on the anticipated size. We will leverage the existing process PHIO has for its Community Development Fund for local, evidence- based health improvement activities. Activities will be monitored and reported quarterly as a component of our dissemination activities to our community partners and the CDCC, and broader RADx-UP consortium

Program Evaluation and Dissemination

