We will collaborate closely with other RADx-UP projects to share data and adapt processes and continuously communicate with our community partners to assess effectiveness and disseminate research findings. Quantitative approaches will include measurements of provider-level, care process, community-level, and patient-level outcomes. Qualitative approaches will include capturing information via semi-structured interviews, exit surveys, and in-depth program implementation process observations. The goals of the evaluation are to: (1) identify community facilitators and barriers to testing; (2) monitor ethical and social implications of testing; (3) measure the fidelity of the practice implementation support strategy; (4) determine the effectiveness, acceptability, and reach of the implementation support model for disseminating and helping practices to implement SARS-CoV-2 testing protocols; and (5) determine the effectiveness of different testing modalities.

E. Chart Review

1. For those practices that cannot generate performance measure data from the EHR, we will provide a chart abstraction protocol for obtaining performance measures through manual chart abstraction of the practice EHR.
2. More specifically, we will be collecting structured data needed for calculating performance measure from automated measure reports built into the EHR, or where these are not available, but developing a Registry Report to collect the data needed to calculate the performance measures.
3. Only aggregated performance measure data (therefore, deidentified) will be entered into REDCap.

4. Entry of data into REDCap will have user controls and logged access.
5. At the end of the Project, the data will be stored for potential future analysis for 10 years.

F. Biospecimens

No specimens will be obtained from participants except for the limited serology studies performed with our collaborators at the Oklahoma Medical Research Foundation, and only for those with positive POC test results to allow confirmation on other platforms. Participants in the limited serology study will be fully consented to participate in the research study. For all other participants, the only research material will be the data obtained by surveys, direct observation, key informant interviews, and medical record abstraction. Abstractions will be conducted at the practices.

G. Banking/Repository/Database

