We will calculate descriptive statistics for all Aim 1 measures and will perform formal hypothesis testing to compare pre- versus post-implementation provider- level, care process, and patient- level outcomes at the patient and practice levels. In addition to this pre-post analysis, trends in testing rates will be explored. A mixed effects linear regression model will be fit to explore changes in testing rates over time relative to the control period (0 months on intervention), accounting for correlation among repeated measures on the same practice and among practices nested within PFs will be accounted for using random effects.³⁸

Descriptive statistics and qualitative summaries will be reported to summarize the facilitators and barriers to implementation. We will calculate descriptive statistics for all Aim 2 measures. County-wide initiatives to amplify community- based testing that are initiated by CHIOs will be descriptively summarized as a function of county, region, and time period. Patient Survey data and program implementation process observations will be used to understand the influence of internal and external contextual factors on the success of community-based testing events. For qualitative data analyses, we will use software-assisted (NVIVO v12) content analytic techniques. Key informant interviews will be transcribed and evaluated by at least two independent coders. Initial codes will be compared across evaluators and emergent thematic categories will be argued to consensus and graphically represented for a better understanding of their meaning and relationships. Although much of the interviews will be guided by a solid understanding of well-known facilitators and barriers to testing, we will be intentionally open to new or unexpected qualitative findings. A subset of the transcripts (10%) will be chosen at random and coded by another researcher to achieve an inter-rater reliability kappa of at least 90%.³⁹⁻⁴⁰ Disagreements on codes will be resolved by discussion. We will take steps to minimize

potential bias⁴¹ including conducting regular debriefs with members of the evaluation team. To better understand perceptions of the utility, effectiveness, and generalizability of the CATCH-UP program, detailed PF implementation notes will be summarized and analyzed according to the domains of the program model.

N. Data and Safety Monitoring Plan

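### Does the Aim 2 evaluation need a written definition of a successful testing event, and do the event size bands conflict with the 45,000 tests?

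*Protocol*

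**What the plan says.** The sentence at issue is in section M (Statistical Methods) of the protocol and is repeated unchanged in the SAP. Patient Survey data and observations of the implementation process will be used to "understand the influence of internal and external contextual factors on the success of community-based testing events". Shortly before it stands the general rule for this aim: "We will calculate descriptive statistics for all Aim 2 measures". Qualitative content analysis follows.

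Four other places in the protocol bear on what success might mean:

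- Section A, Aim 3, gives the community-level outcomes as "the number of tests conducted by mobile testing units and the resulting test positivity rate". Neither is called success.
- Section D, Scope of Testing (community-based strategy), lists the planned events: "88 small events of 25-50 tests, 66 medium events of 51-100 tests, 44 large events of 100-200 tests", then "33 x-large events of 200-500 tests, and 22 community-level events of > 500 tests". The authors then "anticipate that this aim will result in a minimum of 45,000 viral tests" in the first year.
- Section D, Supporting the CPP, uses event size for resourcing: "Funding will also be provided to partners to staff and supply events based on the anticipated size".
- Section D, Program Evaluation and Dissemination, gives as its first goal to "identify community facilitators and barriers to testing".

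**The concern.** Most quantitative work under Aim 2 only describes. This sentence sets out to explain, and the thing to be explained has no event-level measure, denominator or direction. Positivity is ambiguous as a mark of success: a high value may mean that a hotspot was well targeted or that too few people were tested. Raw test counts depend largely on how big an event was planned to be. If the criterion were picked after the event data had been seen, the account of barriers and facilitators could follow the choice of criterion. A feature of small events, perhaps a rural location, could then pass for a barrier.

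The volume figures appear to add to the problem. All 253 listed events could fall within their bands while the programme total stayed well short of the stated minimum. An event could then succeed by its band while the programme fell short of its total.

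**Working it through.** **Inputs.** The event numbers and bands, and the 45,000, come from Scope of Testing in section D. The top band has no upper limit, so its floor is taken as 501.

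**1. Number of events.** 88 + 66 + 44 + 33 + 22 = 253, which agrees with the protocol's statement of more than 250.

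**2. Totals that the bands allow.** The four closed bands give:

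- lower ends: 88×25 + 66×51 + 44×100 + 33×200 = 16,566
- midpoints: 88×37.5 + 66×75.5 + 44×150 + 33×350 = 26,433
- upper ends: 88×50 + 66×100 + 44×200 + 33×500 = 36,300

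The open band at its floor adds 22×501 = 11,022.

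| Closed bands at | Total, open band at 501 | Open-band mean needed for 45,000 |
|---|---|---|
| lower ends | 27,588 | (45,000 − 16,566)/22 = 1,292 |
| midpoints | 37,455 | (45,000 − 26,433)/22 = 844 |
| upper ends | 47,322 | (45,000 − 36,300)/22 = 395, already exceeded |

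The extreme low case is 45,000 − 27,588 = 17,412 tests short, or 39%. It requires every one of the 253 events to sit exactly at its floor. The figure of 45,000 lies inside the permitted range, and each mean in the last column is met by an open band of more than 500. The bands do not guarantee 45,000, but they do not contradict it.

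**3. How far raw counts could mislead.** Assume that every event exactly meets its plan, with closed bands at midpoint and the open band at a mean of 844. The 154 small and medium events then hold 3,300 + 4,983 = 8,283 tests (53.8 each). The 99 larger events hold 45,000 − 8,283 = 36,717 (370.9 each). Suppose a factor is present at a share *p* of the smaller events and 1 − *p* of the larger ones, with *p* assumed.

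- Mean with the factor = [8,283*p* + 36,717(1 − *p*)] / [154*p* + 99(1 − *p*)]
- Mean without it: exchange *p* and 1 − *p*

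| *p* | Present | Absent | Difference |
|---|---|---|---|
| 0.6 | 19,656.6/132 = 149 | 25,343.4/121 = 209 | 29% fewer |
| 0.7 | 16,813.2/137.5 = 122 | 28,186.8/115.5 = 244 | 50% fewer |
| 0.8 | 13,969.8/143 = 98 | 31,030.2/110 = 282 | 65% fewer |

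Attainment of plan is 100% in every cell. The arithmetic is sound, but three things limit its bearing. The splits and the 844 are assumptions. No passage plans a comparison of raw tests per event with a factor present or absent. And if the factor is spread evenly across the tiers within each size group, as the formula takes it to be, the difference vanishes once events are grouped by size: 53.8 v 53.8 among smaller events, 370.9 v 370.9 among larger ones. Nor does the example reverse a conclusion. It sets an apparent difference against none.

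**The case for a change.** The best case for a change is that even a qualitative account of what drives success must sort events into better and worse, and that fixing the criterion beforehand costs one sentence. Tests performed divided by anticipated size would be an obvious candidate, since partners are funded by that size. On wording, the listed mix does not secure a minimum of 45,000. The Abstract's total of at least 105,000 is the sum of 45,000 and an approximate 60,000, so it is not a true floor.

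Part of this stands. The definition is absent from both documents, and the volume wording is firmer than its inputs.

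The proposed remedy is not clearly better than leaving the matter to the evaluators:

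- An attainment ratio depends on how ambitiously each event was sized, and the documents do not say that the anticipated size is kept as data.
- It says nothing about access to and acceptance of testing, which Aim 2 in section A gives as the purpose of observing these events.
- Scoring cancelled events as zero would add events with no survey respondents, so one of the two named data sources could not help to explain them.

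On the totals, the text already presents them as anticipated or estimated. Scope of Testing says the programme will adapt to outbreaks and need, and it hopes that early successes will attract funding for further events. The list of 253 is therefore not a cap.

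**Conclusion.** No change is needed. The claim of conflicting yardsticks fails because the bands are a planned mix of event sizes, the 45,000 is a forecast of aggregate volume, and anticipated size governs staffing and supplies. None is put forward as a criterion of success, and the figures are compatible.

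What remains is one undefined word in a descriptive and qualitative evaluation. Evaluators can fill that gap sensibly by reporting tests and positivity per event, reading them with event size in view, and saying in the report what they took success to mean. The 29% to 65% differences hold only under the assumed splits and tier means, and for an analysis that the plan does not specify. Softening the volume wording would alter no test, sample size, threshold or result, since none uses 45,000 or 105,000. The judgement would differ if event success became the outcome of a formal model or a go/no-go rule. Nothing in either document proposes that.

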Title of Project: Community-engaged Approaches to Testing in Community and Healthcare settings for Underserved Populations (CATCH-UP)

Principal

Investigator: [name], PhD, Oklahoma Clinical & Translational Science Institute

Co-Investigators: [name]; Department of Family Medicine

[name], MPH; Department of Medical Informatics

[name]; Oklahoma Clinical & Translational Science Institute

Statistical Methods:

Descriptive statistics and qualitative summaries will be reported to summarize implementation process measures (type, dose, frequency, and sequencing of provided support strategies) and the facilitators and barriers of implementation.

We will calculate descriptive statistics for all Aim 1 measures and will perform formal hypothesis testing to compare pre- versus post-implementation provider- level, care process, and patient-level outcomes at the patient and practice levels. In addition to this pre-post analysis, trends in testing rates will be explored. A mixed effects linear regression model will be fit to explore changes in testing rates over time relative to the control period (0 months on intervention), accounting for correlation among repeated measures on the same practice and among practices nested within PFs will be accounted for using random effects.³⁸

Descriptive statistics and qualitative summaries will be reported to summarize the facilitators and barriers to implementation. We will calculate descriptive statistics for all Aim 2 measures. County-wide initiatives to amplify community- based testing that are initiated by CHIOs will be descriptively summarized as a function of county, region, and time period. Patient Survey data and program implementation process observations will be used to understand the influence of internal and external contextual factors on the success of community-based testing events. For qualitative data analyses, we will use software-assisted (NVIVO v12) content analytic techniques. Key informant interviews will be transcribed and evaluated by at least two independent coders. Initial codes will be compared across evaluators and emergent thematic categories will be argued to consensus and graphically represented for a better understanding of their meaning and relationships. Although much of the interviews will be guided by a solid understanding of well-known facilitators and barriers to testing, we will be intentionally open to new or unexpected qualitative findings. A subset of the transcripts (10%) will be chosen at random and coded by another researcher to achieve an inter-rater reliability kappa of at least 90%.³⁹⁻⁴⁰ Disagreements on codes will be resolved by discussion. We will take steps to minimize potential bias⁴¹ including conducting regular debriefs with members of the evaluation team. To better understand perceptions of the utility, effectiveness, and generalizability of the CATCH-UP program, detailed PF implementation notes will be summarized and analyzed according to the domains of the program model.
